Method: The inclusion criteria of this study as follows: (a) age must be greater than or equal to 20 years old, (b) admitted to the ICU and have been intubated for at least 24 hours, (c) awareness of people, time, and place without hearing impairment., (d) be able to communicate in writing., (e) the Glasgow Coma Scale(GCS) score must be equal to or greater than 11(with a vocal response of 1 in the patient post-endotracheal tube placement). The exclusion criteria of this study as follows: (a) history of insomnia, Alzheimer's disease, or depression, (b) routine use of sedative-hypnotic drugs (opioids, benzodiazepines, non-benzodiazepines, antihistamines, and melatonin) before admission, (c) post-operation in the operating room before ICU admission, (d) intensive care delirium screening checklist(ICDSC) score of at least 4 or Confusion Assessment Method for the Intensive Care Unit (CAM-ICU) positive. *Sample:* The sample size for this study is calculated using G*Power 3.1, with an effect size set at 0.25 (Kotrlik & Williams, 2003), $\alpha = 0.05$, and power = 0.8. The minimum required sample size is 58 participants. In statistical analysis, a sample size of 30 is often considered the threshold for a large sample, the total sample size will be 60 participants, with 30 participants in the experimental group and 30 participants in the control group.

Study interventions

This study adopts a convenience sampling method and will be conducted

in the Fifth Department of Internal Medicine ICU at Kaohsiung Chang Gung Memorial Hospital. The study groups are set as follows: the white noise group will receive white noise intervention, while the conventional treatment group will receive standard care. The total sample size of 60 participants will be divided into 6 blocks of 10 participants each, with random assignment generated by a computer. Upon admission to the ICU, patients who meet the inclusion and exclusion criteria will be selected. The principal investigator will fully explain the study's purpose and procedures to the patients, and once informed consent is obtained, the recruitment process will begin. On the first day of enrollment, participants will complete a baseline assessment using the VAS sleep quality scale (T0). Random assignment will then allocate participants to either the Treat (white noise) group or the Control (standard care) group based on the generated block sequence.

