For the white noise group, in addition to receiving standard care, white noise will be introduced from 11 p.m. to 6 a.m. the following morning. A noise-reducing sleep aid device will be placed at the corner of the bedside cabinet, and a decibel meter will be positioned near the patient's head. The volume of the noise-reducing sleep aid device will be controlled between 40-50 decibels. According to a study by Van et al. in 2009, up to 90% of delirium occurs on the third day of ICU admission, so the intervention will be applied

continuously for three nights. The control group will receive standard care. Both groups will complete the VAS sleep quality scale at 6 a.m. on the first day after intervention (T1), the third day (T2), and the fifth day (T3). The total number of assessments will be four, each taking approximately 5 minutes.

Outcome measurements: The Verran and Snyder-Halpern Sleep Scale (VSHSS) was initially developed by Snyder-Halpern & Verran in 1989 to measure the sleep quality of hospitalized patients from the previous night. The internal consistency reliability was found to be 0.82. The original scale consisted of four subscales: sleep fragmentation, sleep disturbance, effective sleep, and compensatory sleep. In 1996, Simpson et al. revised the scale to include three subscales: sleep disturbance, effective sleep, and compensatory sleep. Tranner et al. tested the scale in 2003 with 110 hospitalized and surgical patients, and the Cronbach's α values for the subscales of sleep disturbance, effective sleep, and compensatory sleep were 0.86, 0.80, and 0.63, respectively. In 2007, Fang and Wang translated this scale, and the Cronbach's α values for sleep disturbance, effective sleep, and compensatory sleep were 0.90, 0.72, and 0.64, respectively. The overall internal consistency was 0.84, and the Content Validity Index (CVI) was 1.0.

The scale consists of 15 items, each scored on a 0-100mm visual analog scale, where 0 represents the lowest score and 100 represents the highest. The

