sleep disturbance section contains 7 items, with a total score range from 0 to 700. A lower score indicates more severe sleep disturbance. The effective sleep section contains 4 items, with a total score range from 0 to 400. A lower score indicates less effective sleep. The compensatory sleep section contains 4 items, with a total score range from 0 to 400. A lower score indicates a greater need for compensatory sleep. Since the original author of the scale has passed away, the version of the Verran and Snyder-Halpern Sleep Scale used in this study has been translated and authorized by the publisher.

Statistical Methods: Descriptive Statistics: Personal demographic data and disease characteristics of the study participants will be analyzed. Categorical variables will be presented as frequencies and percentages, while continuous variables will be expressed as means and standard deviations.

Inferential Statistics:Independent samples t-tests or chi-square tests will be used to compare the homogeneity of sleep quality and demographic data between the white noise group and the general care group before the intervention.

Independent samples t-tests will be used to compare the differences in sleep quality pre- and post-intervention between the white noise group and the general care group.

Generalized Estimating Equations (GEE) will be used to compare the

effects of the white noise group and the general care group under the factors of group, time, and the interaction between group and time.

Ethical considerations: Ensuring Non-Disclosure of Participants' Identity and Information: A research code will be used to represent each participant's identity during the study, ensuring that the participant's name, ID number, address, medical record number, or any other personal information will not be disclosed during the research process.

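### The GEE names no treatment term; if pre-randomisation T0 is a level of time, the group term is not the treatment effect, and the T0 means should be constrained equal

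*Combined protocol and SAP*

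**What the plan says.** In the combined protocol and SAP, the last item under Statistical Methods (Inferential Statistics) is a GEE comparing the "effects of the white noise group and the general care group under the factors of group, time, and the interaction between group and time". That is the whole specification. The levels of time, the reference visit, the coding, any covariate and the term that tests treatment are not given.

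The visit schedule is under Study interventions. On the day of enrolment "participants will complete a baseline assessment using the VAS sleep quality scale (T0"), and only afterwards: "Random assignment will then allocate participants to either the Treat (white noise) group or the Control (standard care) group". Further ratings follow "on the first day after intervention (T1), the third day (T2), and the fifth day (T3"). The section then adds: "The total number of assessments will be four, each taking approximately 5 minutes".

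The same statistical section also plans baseline homogeneity tests and independent-samples t-tests of pre- and post-intervention differences between the arms.

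**The concern.** T0 precedes allocation, so its true between-arm difference is zero by design. If T0 is one of the levels of time, a group term estimated over those levels mixes a visit that treatment cannot affect with three that it can, or, under one common coding, reflects that visit alone. Group is the first factor listed for comparing the arms, and nothing tells the analyst not to read it as the result.

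Two errors could follow. A chance imbalance at T0 could be reported as a group effect, or a diluted group effect could be reported as no benefit. There is also a loss of efficiency: even the term that does carry the treatment effect ignores the fact that the arms share a T0 mean.

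**Working it through.** **Plan's own figure.** The plan gives no figure for any GEE contrast. Its minimum sample size of 58 does not identify one, because the test family is not stated. For example, 58 results from a between-group repeated-measures test with f = 0.25, four visits and correlation 0.25, but also from a five-predictor regression with f² = 0.25. It is not used below.

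**Inputs from the documents.** 30 per arm; effect size 0.25, metric not stated; alpha 0.05, sidedness not stated; T0 before allocation; T1, T2 and T3 after it.

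**Assumptions.** The 0.25 is Cohen's f, so with two groups d = 2 × 0.25 = 0.5 SD. The effect is equal at T1-T3. Correlation ρ between any two visits is exchangeable at 0.3, 0.5 or 0.7. Data are complete, the test is two-sided, and the normal approximation is used.

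**Step 1: what the group term estimates if T0 is a level of time.** The true visit differences are (0, 0.5, 0.5, 0.5) SD.

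- T0 as reference: the T0 difference, expectation 0. It is significant 5% of the time whatever white noise does.
- Averaged over visits (sum coding, or no interaction): (0 + 0.5 + 0.5 + 0.5)/4 = 0.375 SD, which is 3/4 × 0.5. The factor 3/4 relative to the T1-T3 average holds for any pattern over T1-T3.
- T3 as reference: the T3 difference, 0.5 SD, which says nothing about T1 or T2.

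As a check, an exchangeable GEE was fitted to simulated data (30,000 per arm, ρ = 0.5). It gave group coefficients of -0.015, 0.363 and 0.493 under these three codings. With T0 as reference, the interaction coefficients at T1, T2 and T3 were 0.498, 0.507 and 0.508, the full effect.

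**Step 2: precision.** SE = √(v × 2/30), and power = Φ(estimate/SE − 1.96), with v as follows:

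- Four-visit average: v = (1 + 3ρ)/4
- T1-T3 average, T0 unused: v = (1 + 2ρ)/3
- Interaction contrast (T1-T3 average minus T0): v = (1 + 2ρ)/3 + 1 − 2ρ
- Common T0 mean, or T0 as covariate: v = (1 + 2ρ)/3 − ρ²

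At ρ = 0.5:

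- Four-visit average: v = 0.625, SE = 0.204, 0.375/0.204 = 1.84, power 45%.
- T1-T3 average: v = 0.667, SE = 0.211, 0.5/0.211 = 2.37, power 66%.
- Interaction contrast: v = 0.667 + 1 − 1 = 0.667, power 66%.
- Common T0 mean: v = 0.667 − 0.25 = 0.417, SE = 0.167, 0.5/0.167 = 3.00, power 85%.

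| Contrast | Estimate (SD) | ρ = 0.3 | ρ = 0.5 | ρ = 0.7 |
|---|---|---|---|---|
| Group effect averaged over T0-T3 | 0.375 | 56% | 45% | 38% |
| Interaction: T1-T3 average minus T0 | 0.5 | 52% | 66% | 86% |
| T1-T3 average, T0 unused | 0.5 | 76% | 66% | 58% |
| T1-T3 with common T0 mean or T0 covariate | 0.5 | 83% | 85% | 94% |

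**Step 3: why the last row always leads.** The interaction subtracts the T0 difference with weight 1, and the T1-T3 average uses weight 0. The best weight here is ρ. The excess in v is therefore (1 − ρ)² for the interaction and ρ² for ignoring T0.

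**Sensitivity.** If the 0.25 is d instead, the four rows become 18/15/13%, 17/22/33%, 26/22/19% and 31/32/41%. The last row still leads at every ρ.

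**The case against.** A reader might infer that the plan counts T0 as an outcome visit and takes the group main effect as efficacy, so that the GEE as a whole understates or misses the treatment effect. The documents do not support that, for four reasons.

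- T0's place in the model is an inference. The count of four appears in a sentence about assessments and how long each takes, not about model rows. The inference is reasonable, because time is an unrestricted factor and no covariate is named, but it is not written.
- The GEE sentence names the interaction explicitly and does not say that the group term is the efficacy comparison. With T0 as reference, the interaction coefficients are the treatment effects at each visit. A group coefficient near zero is then what that coding should give.
- The group term is not confined to a baseline difference or a diluted effect. With T3 as reference it is the full T3 effect, and with T0 as a covariate there is no dilution.
- The planned pre/post t-tests, if they compare change between arms as is natural, are not diluted either, and the baseline tests would show a large T0 imbalance.

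All of this stands. It removes any claim that the planned analysis loses the effect. It does not settle which term will be reported as the result. The same sentence can yield zero, three quarters of the effect, or the last-visit effect, depending on a coding choice left open. It also does not answer the efficiency point, since the interaction contrast falls short of the common-T0 model at every correlation tried.

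**Conclusion.** The point holds as one of under-specification and lost efficiency, not as proof that the plan tests the wrong quantity. The plan should not leave open which GEE term is the treatment effect. If T0 is a level of time, a group main effect that includes it is not that effect.

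Under the 0.5 SD assumptions, moving from the interaction contrast to a common T0 mean raises power by 31 points at ρ = 0.3 (52% to 83%), 19 at 0.5 (66% to 85%) and 8 at 0.7 (86% to 94%). Against the T0-inclusive group effect the gains are 27, 40 and 56 points. In patients per arm for 80% power at ρ = 0.5, the needs are 70 for the T0-inclusive group effect, 42 for the interaction and 27 for the common T0 mean, with 30 planned.

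The three-quarters factor needs only complete data and averaging over four visits. The power figures also rest on the assumed effect and on an exchangeable correlation. The documents give no SD or correlation, so the ordering is firmer than the percentages. That T0 enters as a level of time is the likely reading, not a stated fact.

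**What to change.** In Statistical Methods, replace the GEE sentence with one that does the following:

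- Keeps T0 in the model with its mean constrained equal in both arms, or models T1-T3 with T0 as a covariate.
- Names the post-randomisation group contrast, averaged over T1-T3, as the treatment test, with visit-specific contrasts at T1, T2 and T3 reported beside it.
- States that a group main effect that includes T0 will not be reported as efficacy.

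T0 should not simply be dropped. At ρ = 0.7 that gives 58% power, against 86% for the interaction already planned and 94% with adjustment.

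The cost is a sentence or two in the methods. No new data, visits or patients are needed.
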